To determine whether the *in vitro* findings on BCR signaling genes were consistent with transcriptional changes in B cells exposed to glucocorticoids *in vivo*, we measured the expression of key BCR signaling genes over time in a cohort of 20 unrelated healthy volunteers who received a single IV dose of methylprednisolone as part of our clinical protocol, 16-I-0126, “Genomic Responses of Human Immune and Non-Immune Cells to Glucocorticoids” (principal investigator: [name]). Consistent with the *in vitro* data, we observed a significant drop in the expression of *CD79B*, which encodes Igβ, a protein required for BCR assembly and for signal initiation after antigen stimulation.^{27,28} In contrast, expression of *CD79A*, which encodes Igα, was not significantly affected. The gene *CR2*, which encodes a key component of the B-cell co-receptor complex that enhances BCR-mediated signaling,²⁹ was also significantly reduced in expression in response to glucocorticoid.

We also observed decreased expression of *BTK*, which encodes a key tyrosine kinase immediately downstream of the BCR complex, and of *BLNK*, which encodes a B-cell adaptor

protein central to BCR signaling. Interestingly, the gene that encodes the key upstream kinase LYN was significantly reduced in expression after glucocorticoid administration *in vivo*, although it had not reached statistical significance *in vitro*, and the opposite was true of the upstream kinase SYK, which emphasizes the importance of studying these phenomena *in vivo* and in multiple unrelated individuals.

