3.1 Description of the Study Design

Potential participants will present to the NIH CC for a screening visit. Objective documentation of the diagnosis of SLE, the specific clinical manifestations, and the level of disease activity will be established. A baseline whole blood sample will be obtained at screening. Each enrolled participant will be randomly assigned to 1 of 2 methylprednisolone dose groups: 1 mg/kg or 250 mg.

All enrolled participants will return for a day-long study visit (“infusion visit”) within 75 days of the screening visit. Following collection of a pre-infusion whole blood sample, participants will receive a single IV dose of methylprednisolone (based on the dose group assignment), infused over 30 minutes. Whole blood samples will then be obtained serially, 2 and 4 hours after the start of infusion.

Participants will be discharged after collection of the 4-hour blood sample, measurement of vital signs, and documentation of any adverse events (AEs). Two follow-up phone calls will be made to document any AEs related to the methylprednisolone. If any AEs that may require treatment are documented on the follow-up phone calls, then participants will be asked to return to the NIH CC’s outpatient clinic for evaluation by the principal investigator.

We propose an adaptive study design, in which we will recruit an initial cohort of 20 participants into each of the 2 dosing groups. After processing the samples from these participants, we will perform differential expression analysis to determine if recruitment of additional participants (up to the accrual ceiling of 100) would affect the biological interpretation of the data. If additional data would be unlikely to change the study outcome, then no further recruitment will be pursued.

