5.4 Randomization

Study participants will be randomized evenly to 2 dose groups. The purpose of randomization in this setting is to produce balanced dose groups where participants are comparable between groups in terms of possible confounding factors such as age, sex, or concomitant medication use. To further ensure that participants are similar in terms of SLE severity between the groups, we will adopt stratified randomization according to their disease activity using the Safety of Estrogens in Lupus Erythematosus National Assessment SLE Disease Activity Index (SELENA/SLEDAI) score on the day of enrollment. Participants will be classified into 1 of 3 disease-severity categories: low (SELENA/SLEDAI score = 0-4), intermediate (SELENA/SLEDAI score = 5-8), or high (SELENA/SLEDAI score > 9). Randomization will be carried out within each category. This stratified randomization method ensures the proportion of participants with high disease activity is the same between the dose groups.

The study statistician will design the randomization scheme. The randomization code list will be maintained by the study statistician and the study coordinator.

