Based on the data from our previous study of healthy volunteers (protocol 16-I-0126) and a bootstrap procedure, with a sample size of 20 we can detect differentially expressed genes from 0 to 2 hours after glucocorticoid infusion with a median of 0.45 log₂ fold change at a significance level of 0.05 after adjusting for multiplicity, and 0.62 log₂ fold change from 0 to 4 hours. In SLE patients, there may be higher variability in the data than what we observed in healthy volunteers. Meanwhile, the magnitude of gene expression changes is also expected to be higher, given the state of activation of many immune cells in SLE compared to healthy controls. Therefore, we estimate that the proposed initial sample size in this study will be sufficient to detect the genes associated with the effect of glucocorticoids in SLE patients.

To empirically evaluate whether this estimate is correct, we propose an adaptive study design similar to the one we performed on the study with healthy volunteers. Specifically, we will

recruit an initial cohort of 20 participants in each dose group. Based on the observed data from 20 participants, we will then assess the gain in discovery with up to 30 additional participants per group. We will perform a bootstrap procedure, sampling with replacement up to 50 units from the 20 observed participants in each group to evaluate the improvement in gene detection. For example, if the subset of genes that can be detected as differentially expressed over time and the subset of genes that can be detected as differentially expressed over the 2 doses do not change significantly above a number, then we will stop at that number. If there is change in the gene subsets, but the pathways and the biological interpretation of the data remain unchanged, then additional participants will be unlikely to change the outcome of the study and no further recruitment will be pursued. Due to the adaptive sample size determination, we will again use a nominal significance level $\alpha < 0.05$.

16 Ethics/Protection of Human Subjects

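### The interim bootstrap draws up to 50 units from 20 people, so the projected growth in gene lists is not a valid estimate of what new participants would add

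*Combined protocol and SAP*

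**What the plan says.** Section 3.1 sets the purpose of the interim look: "to determine if recruitment of additional participants (up to the accrual ceiling of 100) would affect the biological interpretation of the data". Section 15.6 gives the method. After 20 participants per group, "we will then assess the gain in discovery with up to 30 additional participants per group", and the tool is a bootstrap: "sampling with replacement up to 50 units from the 20 observed participants in each group to evaluate the improvement in gene detection".

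Two ways to stop follow. The first is introduced as an example: recruitment ends at a given size if the list of genes changing over time and "the subset of genes that can be detected as differentially expressed over the 2 doses do not change significantly above a number". The second allows stopping even when the lists still move: "If there is change in the gene subsets, but the pathways and the biological interpretation of the data remain unchanged".

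The section does not say how a gene is scored across resamples, how many resamples are drawn, what amount of change counts, or whether the procedure is compared with a run on data without signal.

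**The concern.** Fifty units stand for 20 observed plus 30 new people, but all 50 come from the same 20. A chance deviation in those 20 is carried into every resample as if it were a real effect, while the standard error shrinks with n. Null genes therefore cross the threshold more often as n rises, and a list can lengthen when new people would add nothing.

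At stake is the decision to recruit up to 2 x 30 = 60 more people, in research that Section 8.2 says is not meant to benefit them. This bootstrap is the only quantitative basis that the plan gives for that decision.

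**Working it through.** **Inputs from the documents.** 20 per group, up to 30 more, up to 50 draws (Section 15.6); ceiling 100 (Section 3.1); Benjamini-Hochberg at 5% (Section 15.3).

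**Assumptions, not in the documents.** 10,000 genes, t-tests in place of DESeq2, and the responder shares and effect sizes shown below.

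**The plan's own figures.** 2 x (20 + 30) = 100 matches the ceiling. The 0.72 SD detectable effect reproduces by normal approximation: (1.960 + 1.282)/√20 = 0.725, with power at 0.72 of Φ(0.72 x √20 − 1.960) = 89.6%. The fold changes quoted from the healthy-volunteer bootstrap cannot be checked, because those data are not given.

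**Step 1: one null gene.** In SD units the observed mean has variance 1/20 around zero, and a resample mean of n draws has variance 1/n around the observed mean. The test statistic therefore has variance n x (1/20 + 1/n) = 1 + n/20. For the dose contrast, (n/2) x (2/20 + 2/n) gives the same result. The nominal 5% test rejects with probability 2Φ(−1.96/√(1 + n/20)):

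- n = 20: 16.6%
- n = 30: 21.5%
- n = 40: 25.8%
- n = 50: 29.5%

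This does not depend on the share of responsive genes. A separate simulation gave about 31% at n = 50, against 5% with 50 real people. Fifty draws hold on average 20 x (1 − 0.95^50) = 18.5 distinct people.

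**Step 2: gene lists.** Counts at n = 20 and n = 50, from 12 trials of 100 resamples. The average score is the mean list length over resamples; the strict score keeps genes called in at least 95% of resamples.

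| Setting | Real participants | Average | Strict |
|---|---|---|---|
| Dose, no difference | 0 to 0 | 211 to 1,669 | 0 to 121 |
| Time, 10% of genes at 2 SD | 1,044 to 1,048 | 1,534 to 2,788 | 1,004 to 1,174 |
| Time, 30% at 2 SD | 3,104 to 3,107 | 3,676 to 4,653 | 3,006 to 3,180 |
| Time, 50% at 2 SD | 5,122 to 5,130 | 5,609 to 6,307 | 5,006 to 5,151 |
| Time, 10% at 0.72 SD | 423 to 1,030 | 965 to 2,678 | 128 to 903 |
| Time, 30% at 0.72 SD | about 2,000 to 3,100 | 2,549 to 4,450 | 635 to 2,506 |

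A majority score (called in more than half of resamples) gives 10 to 1,045 in the first row and 1,080 to 2,176 in the second.

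In the 0.72 SD rows the strict lists are shorter than the real ones at both sizes, but they grow too fast: for 10% responders 903/128 is +605%, against a real 1,030/423, or +143%. The average count also overstates growth there: 2,678/965 is +178%.

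**Step 3: sensitivity.** Pooling the variance over all genes, the extreme of information sharing, leaves the no-difference dose list at 263 to 1,645. Correlation of 0.3 between genes gives 211 to 1,627. The bias sits in the mean, so steadier variances do not remove it.

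**Step 4: what a null run and subsampling can show.**

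- *Dose list, strict score at n = 50, 19 unstratified permutations, 20 trials.* With no difference: 129 genes against 134 permuted, flagged in 0 of 20 trials (2 of 20 with correlation 0.3). With 2% of genes differing by 0.72 SD: 209 against 134, flagged in 20 of 20 (17 of 20 with correlation).
- *Time list, 10% at 2 SD, strict score.* The list grows from 1,003 to 1,195, and the null run from 0 to 137. The excess is 192 − 137 = 55 genes, while real growth in Step 2 is 4. The null run does not size the gain.
- *Subsampling without replacement at 8, 12, 16 and 20.* The saturated 10% list reads 918, 1,044, 1,046, 1,044, which is flat. A list with 10% at 1.0 SD ends 734, 918 (+25%) where the real gain to 50 is +14%. One with effects spread as Normal(0, 1 SD) in 30% of genes ends 1,432, 1,630 (+14%) where it is +36%. The sparse dose effect reads 0, 0, 1, 3, although real data reach about 106 at n = 50.

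**The case against.** The strongest reply is that the gene-list rule is only an example, and that the pathway limb can stop recruitment when the lists keep changing. That stands. It means the bias need not push the decision one way. It does not repair the projection, because pathways read from the resampled lists inherit their errors.

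A second reply is that the settings are unfavourable. A 10% share may be low: the in vitro counts in Section 1.1 imply at least (5,184 + 2 x 5,458 + 9 x 23)/9, or about 1,812, responsive transcripts per cell type on average, which is 18% of the assumed 10,000. Relative inflation does shrink as the share rises, but at 50% the average count still adds about 700 genes where real people add 8. An exactly null dose contrast is a limiting case. It is still plausible, since Section 1.1 calls the extent of dose differences unclear and Section 1.3 describes near-saturation of the receptor at 30-100 mg/day prednisone-equivalent.

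Third, the plan never says that duplicates are analysed as separate people. True, but no other handling is described, and 50 units are used to represent 50 participants.

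Some stronger readings do not hold:

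- *Projected lists are always too long.* They are not: strict scoring makes weak-effect lists too short.
- *A strict score would cure the problem.* It does not. It projects +130% for 10% of genes at 1.0 SD, where the real gain is +16%, but only +82% for the spread effects, where it is +34%.
- *The average count ranks cases backwards.* At a fixed responder share it puts saturated lists below unsaturated ones (30% share: +27% against +75%).
- *The earlier study shows how the rule behaves.* Section 15.6 says "we propose an adaptive study design similar to the one we performed on the study with healthy volunteers", and Section 1.1 describes "a cohort of 20 unrelated healthy volunteers who received a single IV dose of methylprednisolone", but the documents do not say why that cohort ended at 20.

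**Conclusion.** The concern holds in a limited form. Raw growth from 20 to 50 resampled units is not a valid estimate of the gain from new participants under any score tried, and the plan chooses none. The null rejection rates of about 17% and 29% follow from the sampling scheme. The list counts are illustrative and rest on the assumed gene number, responder shares and effect sizes; DESeq2 was not run.

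The harm is confined to the recruitment decision. A reader might infer that the trial will over-recruit, or that its published lists will be full of false genes. Neither follows: no simulation was carried through to a stop-or-continue decision including the pathway limb, and the final Benjamini-Hochberg list comes from real participants. This should be fixed before the interim look.

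**What to change.** In Section 15.6:

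1. State that with-replacement samples larger than 20 are not read as a projection of new participants.
2. If the bootstrap is kept, fix the resample score before the interim look and count only growth beyond a null run of the same procedure. For the dose list, permute dose labels within the SELENA/SLEDAI strata, because Section 5.4 says "Randomization will be carried out within each category". For time lists, swap pre- and post-infusion labels within participant. Say that this shows whether signal is present, not how much would be gained.
3. Report learning curves subsampled without replacement, up to n = 20, as a check on whether the time lists have flattened. The sponsor should set the threshold in advance. Note that the curves neither rank nor size the later gain, and that a flat, near-empty dose curve is not by itself a reason to stop.
4. Read the pathway limb from the calibrated lists.

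The cost is SAP wording and modest computing on data already collected, with no extra participants or samples. The drawback is that none of this directly estimates how many participants to add. The stratified permutation was not itself simulated here, so it should be tried before it is adopted.

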16.1 Informed Consent Process

Informed consent is a process where information is presented to enable persons to voluntarily decide whether or not to participate in research. It is an ongoing conversation between the human research participant and the researchers that begins before consent is given and continues until the end of the participant's involvement in the research. Discussions about the research will provide essential information about the study and include: purpose, duration, experimental procedures, alternatives, risks, and benefits. Participants will be given the opportunity to ask questions and have them answered.

The participants will sign the informed consent document prior to undergoing any research procedures. The participants may withdraw consent at any time throughout the course of the trial. A copy of the informed consent document will be given to the participants for their records. The researcher will document the signing of the consent form in the participant's medical record. The rights and welfare of the participants will be protected by emphasizing to them that the quality of their medical care will not be adversely affected if they decline to participate in this study.

We anticipate the enrollment of Spanish-speaking participants in this study. The English language consent document will be translated in full into Spanish by the NIH Library. For Spanish-speaking participants, the Spanish language consent form will be presented by the investigator through an interpreter, unless the investigator is fluent in Spanish.

Two Step Consenting Process

In certain cases, when prospective participants would like to learn additional details about the study before coming to the NIH (e.g., due to geographical distance or other logistical and personal reasons), we would like to do a two-step informed consent process. In the first step, we will either mail or email the informed consent document to the patient; this will be followed by a

telephone call or videoconference, to go over the informed consent form document orally. For patients who agree to participate at that point, the second step will involve scheduling a screening visit at the NIH Clinical Center. As with any other screening visit, a member of the study team will then answer any additional questions and obtain the patient's written signature in the informed consent form. This informed consent process will then be documented in the subject's medical records.

16.2 Participant Confidentiality

All records will be kept confidential to the extent provided by federal, state, and local law. The study monitors and other authorized individuals may inspect all documents and records required to be maintained by the investigator, including but not limited to, medical records. Records will be kept locked and data will be coded. Any personally identifiable information maintained for this study will be kept on restricted-access computers and networks. Personally identifiable information will only be shared with individuals authorized to receive it under this protocol. Individuals not authorized to receive personally identifiable information will be provided with coded information only, as needed. Clinical information will not be released without written permission of the participant, except as necessary for monitoring by the IRB, NIAID, and the Office for Human Research Protections.

16.3 Participation of NIH Employees

NIH employees may participate in this protocol. We will follow the Guidelines for the Inclusion of Employees in NIH Research Studies and will give each employee a copy of the "NIH Information Sheet on Employee Research Participation."

For NIH employees:

- NIH staff may be a vulnerable class of participants.
- Neither participation nor refusal to participate will have an effect, either beneficial or adverse, on the participant's employment or work situation.
- The employee participant's privacy and confidentiality will be preserved in accordance with NIH CC policies, which define the scope and limitations of the protections.
- For NIH employee participants, consent will be obtained by an individual independent of the employee's team. Those in a supervisory position to any employee and co-workers of the employee will not obtain consent.
- The importance of maintaining confidentiality when obtaining potentially sensitive and private information from co-workers or subordinates will be reviewed with the study staff at least annually and more often if warranted.

17 Data Handling and Record Keeping

17.1 Data Capture and Management

Study data will be maintained in CRIMSON and collected directly from participants during study visits and telephone calls, or will be abstracted from participants' medical records. Source documents include all recordings of observations or notations of clinical activities and all reports and records necessary to confirm the data abstracted for this study. Data entry into CRIMSON will be performed by authorized individuals. The investigator is responsible for assuring that the data collected are complete, accurate, and recorded in a timely manner.

